7.2. Protocol Deviations

Subject-specific protocol deviations will be summarized by the reason for the deviation, the deviation category, treatment group, disease severity and (separately) geographic region for all subjects (Table 7 and Table 8). Supplementary protocol deviation summaries will also be generated (e.g. major deviations, non-subject specific deviations). All subject-specific protocol deviations and non-subject specific protocol deviations will be included in listings (Listing 3 and Listing 4).

8. EFFICACY EVALUATION

8.1. Primary Efficacy Analysis

8.1.1. Primary Analyses

The primary analysis uses the stratified log rank test to compare treatment to control through Day 29 with respect to time to recovery, as defined in Section 3.3. Stratification is based on moderate versus severe disease at baseline. As noted in Section 3.3, all deaths within 29 days will be considered censored at Day 29 with respect to time to recovery. Conceptually, a death corresponds to an infinite time to recovery, but censoring at any time greater than or equal to Day 29 gives the same answer as censoring at Day 29; both correspond to giving deaths the worst rank.

Let MM and S denote the Moderate and Severe subgroups, respectively. The z-score associated with the stratified log rank test is

$$Z = \frac{\sum_{MM}(O_i - E_i) + \sum_S(O_i - E_i)}{\sqrt{\sum_{MM} V_i + \sum_S V_i}}$$

The sums are over recovery times t_i in the moderate and severe subgroups, O_i is the number of treatment arm participants recovering at time t_i , and E_i and V_i are the null expected value and variance of the number of treatment recoveries calculated using the hypergeometric distribution. Specifically, if n_{Ti} and n_{Ci} denote the numbers of patients 'at risk' in the two arms in a given stratum at t_i , and r_i is the total number of recoveries at t_i , then $E_i = r_i n_{Ti} / (n_{Ti} + n_{Ci})$ and $V_i = r_i (n_i - r_i) n_{Ti} n_{Ci} / [n_i^2 (n_i - 1)]$, where $n_i = n_{Ti} + n_{Ci}$. The O_i , E_i , and V_i are computed separately within the moderate and severe strata.

As noted in Section 6.6.2, to maintain an overall two-sided type-I error rate of 0.05, the Lan-DeMets spending function analog of the O'Brien-Fleming boundary will be used to derive the cumulative error spending and boundaries for the interim analysis.

For the final analysis, the log rank test will be performed using the pseudocode provided in Section 6.1. The following pseudocode can be used to compute the bounds for the final analyses and compare to the calculated log-rank statistic. The Boundaries dataset will contain the updated boundaries calculated from the interim analyses using the actual information levels observed at the interim analysis.

```

data Params_LogR;
  set logrankp(rename=(Statistic=Estimate));
  if Variable='TreatmentVariable';
  _Scale_='Score';
  _Stage_= AnalysisNumber;
  keep Variable _Scale_ _Stage_ StdErr Estimate;
run;

proc seqtest Boundary=Boundaries
  Params(Testvar=TreatmentVariable)=Params_LogR
  infoadj=prop
  boundaryscale=score
  ;

```

```
ods output Test=FinalResults ParameterEstimates = LogHRest;  
run;
```

If the trial is stopped at the interim analysis, then to derive the p-value, hazard ratio estimate, and confidence interval for the early and final analysis sets, stage-wise ordering of the sample space will be used [5]. The resulting p-value, median unbiased estimate, and confidence interval will be presented in the final report. If the trial is not stopped early, then the fixed sample estimates of the statistics using an alpha level of 5% will be computed and reported for the final analysis. The SAS pseudocode above provides estimates for the log hazard ratio and so the estimates will be exponentiated and reported.

The primary analysis will be performed in the ITT analysis population. The treatment hazard ratio estimate and confidence interval and p-value from the stratified log rank test will be presented (Table 15). The median time to event and 95% confidence interval will be summarized by treatment arm and disease severity. In addition, stratum-specific estimates of the treatment hazard ratio from Cox models run within each of the disease severity strata will be presented. Kaplan-Meier curves for each treatment arm will be presented, supplemented with the hazard ratio estimate, p-value, and the number of subjects at risk in each arm and severity stratum at Days 1, 3, 5, 7, 11, 15, 22, and 29 (Figure 2).

Subject listings of the ordinal scale results by day will be generated (Listing 5).

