3.3.2. Recovery and Time to Recovery

The primary efficacy outcome measure is the time to recovery. Recovery will be defined as having a value of 1, 2, or 3 on the clinical status 8-point ordinal scale. The time to recovery will be defined as the elapsed time (in days) from randomization to the earliest day at which a subject

reaches recovery. Note that since clinical status assessments are recorded as defined in Section 4.3, the day that is being assessed (not necessarily the day the response is collected) will be used to determine the timing of events. For example, a subject with a score of 5 recorded on Days 1 - 3 and a score of 3 recorded on Day 4 will have a time to recovery equal to 3 days. It is also possible that a subject has a clinical status score > 3 reported for a particular day but was subsequently discharged on the same day. Such cases will be reviewed by the NIAID Medical Officer to make the determination of whether the subject should be considered recovered in analyses. Subject data to be reviewed as part of this determination will include the reported clinical status scores while hospitalized, where the subject was discharged to (e.g. private residence, rehabilitation facility, long-term care/nursing home), and any information regarding readmittance.

Any subjects that are lost to follow-up or terminated early prior to an observed recovery will be censored at the day of their last observed assessment. Subjects who complete follow-up but do not experience recovery will be censored at the day of their Day 29 visit. All deaths within Day 29 (and prior to recovery) will be considered censored at 28 days. Note that we do not expect many subjects to worsen after discharge.

However, we will evaluate whether any discharged subjects subsequently experience a worse clinical status and sensitivity analyses will be conducted accordingly. For these analyses, subjects who recover but are later re-admitted for COVID-19 will not be considered a recovery but will instead be censored at 28 days.

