6. GENERAL STATISTICAL CONSIDERATIONS

6.1. General Principles

This is a double-blind, placebo controlled randomized trial with a two-sided type I error rate of 0.05. Secondary hypotheses have been ordered according to relative importance. These will be described according to the appropriate summary statistics, e.g.

- Percentages/proportions/odds ratios for categorical data. For tabular summaries of percentages/proportions, the denominator (e.g. number of subjects with non-missing data) will be displayed.
- Means, median, and range for continuous data, median for time-to-event data.

Confidence intervals will be generated; for the primary analysis, the confidence level will take into account the group-sequential design of the trial (see Section 6.6 and Section 8.1) whereas 95% confidence intervals will be generated for secondary and exploratory outcomes. For hazard ratio and odds ratio estimates, Wald confidence intervals will be used. For other efficacy outcomes, Wilson or Score confidence intervals will be used. For safety outcomes, exact (e.g. Clopper-Pearson) confidence intervals will be used.

When calculating treatment effects (e.g. differences, hazard ratios, odds ratios) and when using treatment arm as a covariate in regression modeling, the remdesivir+placebo arm will be used as the reference group. For regression modeling that uses strata variables defined in Section 6.4, the first stratum listed for each variable in that section will be used as the reference group.

For the final time-to-event analyses, the following SAS pseudocode will be used to perform stratified analyses to generate stratum-specific median time to event estimates and confidence intervals, stratum-specific Kaplan-Meier curves, and to perform the log-rank test. For any unstratified analyses, code can be used after the removal of the `strata ... ;` line.

```
proc lifetest data=dataset plots=(s);
  time TimeVariable * CensorVariable(1);
  strata StrataVariable;
  test TreatmentVariable;
run;
```

Note that the interim efficacy analyses will be performed using R. For all interim and final analyses, the software used will calculate the log rank statistic using the formula in Section 8.1.1.

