6.5. Missing Data

All attempts will be made to collect all data per protocol. Any data point that appears to be erroneous or inexplicable based on clinical judgment will be investigated as a possible outlier. If data points are identified as outliers, sensitivity analyses may be performed to examine the impact of including or excluding the outliers. Any substantive differences in these analyses will be reported.

For time to event outcomes, subjects who are lost to follow-up or terminate the study prior to Day 29 and prior to observing/experiencing the event will be censored at the time of their last observed assessment. Subjects who die prior to observing/experiencing the event will be censored at Day 29.

For the analysis of the key secondary outcome, subjects who are discharged but are subsequently re-admitted prior to Day 15 without a reported clinical score, their clinical score will be imputed at 7, which is the highest value for a hospitalized subject.

For the analyses of the secondary outcomes that involve clinical score (i.e. the key secondary outcome and time to improvement), if a subject is discharged from the hospital without a previously or concurrently reported clinical score of 1 or 2, then their clinical score at the time of discharge will be imputed as 2, which is the highest value for a non-hospitalized subject. If a subject terminates early from the study while they are hospitalized or completes the study while still hospitalized, the last observed clinical score assessment will be used as their final assessment.

For the modified version of the ordinal score described in Section 4.3, if a subject is discharged from the hospital without a previously or concurrently reported clinical score of 2 or 3, then their clinical score at the time of discharge will be imputed as 3, which is the highest value for a non-hospitalized subject.

For the analyses of the secondary outcomes described in Section 3.3, the following imputation rules will be used for subjects who are lost to follow-up, terminate early from the study, or do not have further outcome data available after discharge for any reason:

- Days of Non-invasive ventilation/high-flow oxygen:

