6.6.2. Interim Efficacy Review

An interim efficacy analysis will be conducted after approximately 33% of total information has been reached. The information fraction at an interim analysis will be computed as $t = r/723$ where r is the number of recoveries by the time of the data freeze date for the interim analysis. The Lan-DeMets spending function analog of the O'Brien-Fleming boundary will be used to monitor the primary endpoint using an overall two-sided type-I error rate of 0.05. Specifically, two one sided boundaries are constructed at level 0.025 using the spending function

$$\alpha^*(t) = 2[1 - \Phi\{2.241/t^{\frac{1}{2}}\}],$$

where Φ is the standard normal distribution function. Lan-DeMets software from the University of Wisconsin, now available in the R package 'lbound', will be used to calculate boundaries.

Conditional power will be presented as an additional guide to the DSMB. Conditional power allows computation of the probability of obtaining a statistically significant result by the end of the trial given the data accumulated thus far, incorporating and assuming a hypothesized treatment effect (e.g., the treatment effect assumed for sample size determination) thereafter. If conditional power is less than 20% under the original trial assumptions, consideration should be given to stopping the trial.

The unblinded statistical team will prepare these closed session reports for DSMB review and recommendations. Analyses will be presented with blinded codes for treatment arms to protect against the possibility that the DSMB report may fall into the wrong hands. A DSMB Charter will further describe procedures and membership. An additional document on statistical issues related to monitoring may be provided to the DSMB prior to interim analyses.

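### Interim look only: holding deaths at risk to Day 29 over-fills the late risk sets at the data freeze and shifts the interim Z slightly; SAP 6.6.2 needs a censoring rule for that cut

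*SAP*

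**What the plan says.** Three SAP sections put a death before recovery at the end of the follow-up window:

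- 8.1.1 (primary analysis): "all deaths within 29 days will be considered censored at Day 29 with respect to time to recovery".
- 3.3.2 (endpoint definition): "All deaths within Day 29 (and prior to recovery) will be considered censored at 28 days".
- 6.5 (time-to-event outcomes generally): "Subjects who die prior to observing/experiencing the event will be censored at Day 29".

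Day 29 and 28 days after randomization are the same point. None of the three mentions an interim cut. SAP 8.1.1 justifies the rule by noting that any censoring time at or beyond Day 29 gives the same result and ranks deaths worst.

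The same statistic is used at both looks. SAP 6.1: "For all interim and final analyses, the software used will calculate the log rank statistic using the formula in Section 8.1.1". SAP 6.6.2: "An interim efficacy analysis will be conducted after approximately 33% of total information has been reached", with the information fraction based on "the number of recoveries by the time of the data freeze date for the interim analysis".

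For living, unrecovered patients, SAP 3.3.2 covers two groups. Those lost or terminated early "will be censored at the day of their last observed assessment". For completers, "Subjects who complete follow-up but do not experience recovery will be censored at the day of their Day 29 visit". It does not mention patients still in follow-up at a freeze. SAP 6.2.2 refers to a separate DSMB guidance document and a DSMB report shell, neither of which is available here.

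**The concern.** The worst-rank argument in SAP 8.1.1 needs every patient to have 28 days of possible follow-up. That is so at the final analysis. It is not so at one third of the recoveries in a trial expected to enrol over 2–3 months (Protocol, Appendix B 1.1).

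Take two patients randomized 10 days before the freeze. One is alive and unrecovered, and leaves the risk set at 10 days because nothing later can be observed. The other died at 5 days and stays in the risk set to 28 days. From 11 to 28 days, that entry cohort contributes its deaths to the 8.1.1 at-risk counts and nobody who could recover. This has two effects:

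- The arm with more recent deaths has its late at-risk count inflated more, so its expected recoveries are too high and its result looks worse.
- Adding deaths to both arms pulls the late at-risk ratio towards 1:1, which works slightly against the arm that is recovering faster.

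Both effects come on top of the worst-rank penalty that the plan intends, and both depend on the calendar pattern of accrual. The DSMB would be reading a Z, a rate ratio and a conditional power that are not quite those of the planned final test.

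**Working it through.** **Reproducing the plan's base.** SAP Section 5: E = 4(1.96 + z_β)²/{ln θ}². With θ = 1.25 and z_β rounded to 1.04, E = 4 × 3.00²/0.2231² = 723, as stated. 723/0.70 = 1033, against the stated 1032. One third of 723 is 241 recoveries.

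**Interim boundary.** SAP 6.6.2 at t = 1/3: 2[1 − Φ(2.241/√(1/3))] = 0.000104 one-sided, so the boundary is Z = 3.71.

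**Simulation.** 3,000 trials per scenario, with the 8.1.1 log-rank (single stratum) and the freeze at the 241st recovery. From the documents: 1:1 allocation, accrual of 60–90 days, 70% recovery by 28 days, a control median of 11 days and mortality of 8.0% versus 11.6% (both from the ACTT-1 preliminary review). Assumed: uniform entry, Weibull recovery, deaths among non-recoverers at uniform (or, where marked, gamma) times, and the other mortality pairs. Living patients are censored at the freeze. Each simulated trial is analysed twice: with deaths at 28 days (as written), and with deaths at min(28 days, freeze minus randomization).

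About 415–485 patients are enrolled at the freeze, which falls about 27–38 days into accrual. Share of the risk set already dead:

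| Days since randomization | As written | Cut at freeze |
|---|---|---|
| 14 | 19–25% | 15–21% |
| 21 | 33–46% | 23–28% |
| 28 | 52–99% | 4–38% |

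Shift in mean interim Z, as written minus cut at freeze (positive favours treatment; standard error about 0.002):

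| True ratio | Deaths, treatment vs control | Accrual, days | Shift |
|---|---|---|---|
| 1.00 | 8.0% vs 11.6% | 60 / 90 | +0.050 / +0.044 |
| 1.00 | 8.0% vs 11.6% (gamma) | 75 | +0.062 |
| 1.00 | 11.6% vs 8.0% | 75 | −0.049 |
| 1.00 | 5% vs 15% | 60 / 90 | +0.143 / +0.127 |
| 1.00 | 10% vs 10% | 90 | −0.002 |
| 1.25 | 8.0% vs 11.6% | 60 / 90 | +0.021 / +0.016 |
| 1.25 | 5% vs 15% | 75 | +0.114 |
| 1.25 | 10% vs 10% | 75 | −0.038 |
| 1.25 | 9.5% vs 10.5% | 75 | −0.020 |
| 1.25 | 11.6% vs 8.0% | 75 | −0.088 |

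With no recovery effect, cutting deaths at the freeze returns mean Z to about zero (−0.02 to +0.04, simulation error about 0.018) whatever the mortality split. The two effects roughly add: −0.049 − 0.038 = −0.087, against −0.088 in the last row. Within a single trial the shift has a standard deviation of about 0.09–0.10.

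**Effect on the boundary.** At ratio 1.25, the probability of crossing 3.71 changes by 0.4 points or less in the 8.0%/11.6% cases (either way round), and from 2.1% to 3.0% at 5% versus 15%.

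**Effect on conditional power.** CP = 1 − Φ{[1.96 − z√t − θ(1 − t)]/√(1 − t)}, with t = 1/3 and drift θ = ln(1.25)√(723/4) = 3.00.

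- At z = 0, shifts of 0.05 and 0.14 move CP from 52.0% to 53.4% and 55.9%.
- CP equals 20% at z = −1.26, so the reading changes only if Z falls within the shift of that value.
- With no recovery effect the chance is about 0.180 × 0.05 = 0.9% to 0.180 × 0.14 = 2.5%, where 0.180 is the normal density at 1.26.
- At ratio 1.25, mean Z is about 1.7, so −1.26 lies about 3 SD away and the chance is well under 0.1%.

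Direct simulation agrees: 1–3% of runs with no recovery effect and about 0–0.2% at ratio 1.25.

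**The case against.** The strongest reply is that nothing of consequence changes. At the only mortality contrast in the documents, the shift is 0.04–0.06 with no recovery effect and about 0.02 at ratio 1.25 when the treated arm has fewer deaths, against a boundary of 3.71. Conditional power below 20% only prompts consideration of stopping. The DSMB also sees safety data in real time, so it need not read mortality out of the recovery statistic. All of this stands, and it makes the point minor.

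It is also fair that the worst-rank rule is meant to let mortality count against an arm. That stands too; only the accrual-dependent excess is at issue.

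Censoring living patients at the freeze is inferred, because SAP 3.3.2 does not address them. The inference is hard to avoid, since nobody is observed past the freeze. But the DSMB documents may already hold an interim rule, so its absence can be asserted only for the SAP.

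A reader might infer three stronger things that the documents do not support:

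- **That a futility reading could easily be tipped.** At z = −1.20 a shift of −0.15 does take conditional power from 21% to 18%. But a shift that large needs a mortality imbalance well beyond the documents' own, and under the planned ratio such a z lies nearly 3 SD below its expected value.
- **That the bias always runs against the arm with more deaths.** At ratio 1.25 with 9.5% versus 10.5% deaths it runs against the arm with fewer.
- **That type I error or the final result is compromised.** With no effect on recovery or death the shift is about zero, and at the final analysis the two rules coincide.

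**Conclusion.** The point holds as a minor one. As written, the Day 29 rule for deaths, applied through the 8.1.1 log-rank at a data freeze, gives an interim statistic that is slightly off target. The SAP's stated reason for the rule is valid only with complete follow-up. The shift in mean Z is about 0.05 at 8.0% versus 11.6% mortality and about 0.14 at 5% versus 15% with no recovery effect, plus about 0.04 against the faster-recovering arm at ratio 1.25. DSMB decisions would rarely differ.

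These sizes rest on uniform accrual over 60–90 days, the recovery and death-time models above, a single stratum, and living patients censored at the freeze. The mechanism does not depend on those modelling choices, but it does require that living patients leave at or before the freeze.

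**What to change.** Add to SAP 6.6.2, or cite the DSMB document if it already says this:

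> At an interim analysis, a subject who died before recovery is censored at the earlier of 28 days and the time from randomization to the data freeze date. Living, unrecovered subjects still in follow-up are censored at the earlier of 28 days and their last assessment on or before the same freeze date, with status data complete to that date.

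The second sentence is needed. If data-entry lag takes living patients out before the freeze while deaths stay in until it, part of the asymmetry remains. Keep the Day 29 rule for the final analysis.

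The cost is two sentences, a small change to the interim code, and a check that status data are complete at the freeze. The final analysis does not change.

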8.1.2. Supplemental and Sensitivity Analyses

For all supplemental and sensitivity analyses of the primary outcome, p-values may or may not be reported, and 95% confidence levels will be used for confidence interval estimates.

The primary analysis will be repeated in the As Treated analysis population where subjects who are not treated will be censored at enrollment. The tabular and graphical summaries described in the previous section will be replicated for this As Treated analysis.

Sensitivity analyses will be performed using Cox proportional hazards models to estimate the hazard ratio. First, an ITT analysis will be performed in which subjects who die prior to recovering are treated as experiencing a competing risk in the Fine-Gray proportional hazards regression model. Second, a Cox model will be fit with binary indicators for treatment group and disease severity Moderate vs. Severe [separate models for randomized stratum and actual stratum] as well as a treatment * disease severity interaction term. The models will be fit to the ITT analysis population. The treatment group hazard ratios and CIs will be reported for both sets of models and the interaction term p-value will be reported for the interaction models. As requested by the DSMB, a restricted mean survival time analysis will be performed as an exploratory analysis. The restricted mean recovery time estimates will be provided for each treatment group and randomized disease severity stratum as well as the difference in restricted mean recovery time between treatment groups within each of the severity strata (Table 18). Time to recovery will also be explored within prior Remdesivir treatment subgroups (Any Treatment vs. No Treatment) (Table 19).

The primary analysis will also be repeated using the other subgroups defined in Section 6.4 in place of disease severity. Each subgroup will be considered separately and the tabular and graphical summaries described in the previous section will be replicated for each subgroup. The tabular summary will also include results from an analysis of time to recovery controlling for age

and duration of symptoms as continuous covariates and baseline d-dimer and CRP values as continuous covariates. A forest plot will be generated to display the overall treatment hazard ratio estimate and CI from each of the within-stratum analyses (Table 20 and Table 21). These analyses will be performed in the ITT and As Treated populations.

In addition, a forest plot will be generated for the “leave one out” sensitivity analyses described in Section 6.7; hazard ratio estimates and CIs will be provided for each subgroup that leaves a single site out.

An additional sensitivity analysis will evaluate the effect of recoveries that were not sustained as indicated in Section 3.3.2.

As noted in Section 6.4, analyses that take into account concomitant medication will be performed. The primary analysis will be repeated, where subjects who take prohibited medications will be treated as treatment failures and will be censored at the time of medication use.

Two corroborative summaries will also be generated. A summary of the number and percentage of subjects in each treatment group who recovered (and are alive), did not recover (and are alive), and died by Day 29 will be summarized. The summary will also include the numbers and percentages, grouping deaths and non-recoveries together (Table 24). The summaries will also be provided by the duration of symptoms categorizations specified in Section 6.4.

Other censoring techniques and additional analyses of the primary outcome may be performed.

